# 7.3.6. Probability of Experiencing a BILAG A or B Flare

**Endpoint**: The BILAG instrument will be completed at baseline and every follow-up visit, including any Flare or Endpoint visits, during the course of the 60 week study period for all subjects. See Section 7.3.4, *Probability of Experiencing a BILAG A Flare*, for more details on the BILAG assessment.

For each subject, a yes/no variable will be created to indicate whether a subject had at least one BILAG A or B flare, in any body system, by Week 60. Subjects who terminate early from the study prior to experiencing a BILAG A or B flare will be categorized as not experiencing a BILAG A or B flare by Week 60.

The probability of experiencing any BILAG A or B flare will be calculated for each study arm by each body system and overall.

Additionally, for each subject, the total number of visits with a BILAG A or B flare will be tabulated by arm for each body system and overall.

**Analysis**: Analyses analogous to those specified for the primary endpoint (effect estimates and 95% confidence intervals, risk difference, and summaries of increased risk ( $\alpha$ ) vs.% confidence the "true" risk is  $\leq \alpha$ ) will be performed for the probability of experiencing a BILAG A flare by Week 60. See Section 7.2.2, *Primary Analysis of the Primary Endpoint*, for more details on the analyses. Summary tables for BILAG scoring by body system will be provided. The total number of visits that a subject has with a BILAG A or B flare will be summarized by treatment group and overall.

The study day of flare, type (A or B), body system, and number of flares for each subject will also be shown graphically over time by subject and treatment group.

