# 8.3.2.2 Secondary Analyses

All secondary analyses will be conducted in an exploratory fashion with p-values and confidence intervals presented as descriptive statistics with no adjustments for multiple comparisons. Interval estimates will be generated at the 95% confidence level. Analyses will be conducted on the mITT population and the per protocol population.

Analyses described for the primary analysis of the primary endpoint will be repeated using the per protocol population.

In addition, analysis will be conducted in a similar fashion for the secondary endpoints that are probability of experiencing an event including: any SELENA-SLEDAI\* flare by Week 60, any severe SELENA-SLEDAI\* flare by Week 60, any BILAG\* A flare by Week 60, a BILAG\* Renal A flare (for subjects with renal manifestations) by Week 60, and addition of aggressive adjunctive therapy to MMF or a change in MMF therapy to cytotoxic drug due to flare. These analyses will be conducted on the mITT and PP populations.

For the time to event endpoints (time to clinically significant disease reactivation, time to first SELENA-SLEDAI\* flare and time to first severe SELENA-SLEDAI\* flare), graphical summaries of time to event will be generated using Kaplan-Meier survival curves. The Greenwood method will be used to compute confidence intervals.

Descriptive statistics (mean, standard deviation or standard error, median, minimum, maximum and number of subjects in a group) and 95% confidence intervals will be reported for the difference between the treatment groups in cumulative steroid dose at Week 60; change in FACIT fatigue score from baseline to Weeks 24, 48, and 60; change in SF-36® PF and PCS domains from baseline to Weeks 24, 48, and 60; change in LupusQoL-US© from baseline to Weeks 24, 48, and 60, and change in SLICC/DI\* from baseline to Weeks 24, 48, and 60.

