#### 7.3. Secondary Clinical Disease Activity Endpoints

All secondary analyses will be conducted in an exploratory fashion with any p-values and confidence intervals presented as descriptive statistics with no adjustments for multiple comparisons. Interval estimates will be generated at the 95% confidence level. Analyses will be conducted on the mITT population and the PP population.

Version: 1.0 Page 20 of 48

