#### 12. CHANGES TO THE ANALYSES PLANNED IN THE PROTOCOL

[figure not shown]
- Section 7.2. Primary Endpoint. Statistical methods to obtain effect estimates and confidence intervals for the probability of observing clinically significant disease reactivation by 60 weeks have been changed from exact methods for complete data (proportions with Clopper Pearson intervals) to Kaplan-Meier predict-limit estimators to allow for censoring of subjects who terminated early without evidence of disease reactivation.
- 2. Section 7.3.3. Time to First SELENA-SLEDAI Flare: Time to first SELENA-SLEDAI flare has been changed from using withdrawal date to using Day 0 date. This allows us to calculate time to first SELENA-SLEDAI flare in both arms, since the Maintenance arm does not start withdrawal, and is consistent with the timing of the time to disease reactivation endpoint specified in Section 7.3.1.
- 3. Section 7.3.6. Probability of Experiencing a BILAG A or B Flare: This is a new endpoint was added to the SAP by the study team.
- 4. Section 11.1. Interim Analysis: The sample size re-estimation specified if ≤ 10% of the first 80 subjects experienced disease reactivation was not performed. We observed that after 60 weeks of post-randomization, 8 of the first 80 (10%) subjects experienced disease reactivation. Although the rate of disease reactivation was low, the team opted not to re-estimate the sample size. Rates of BILAG and SELENA-SLEDAI flares, which will also be important for evaluating the impact of MMF withdrawal, are higher than 10%. The larger sample size is necessary to improve precision for these important secondary endpoints and will strengthen the primary analysis.

Version: 1.0 Page 36 of 48

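### SAP 7.3.6 defines a BILAG A or B flare endpoint, but its Analysis sentence specifies the between-arm comparison for BILAG A flare, repeating 7.3.4

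*SAP*

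**What the plan says.** The Endpoint paragraph of SAP 7.3.6 creates a yes/no variable for "whether a subject had at least one BILAG A or B flare, in any body system, by Week 60". It also states that "The probability of experiencing any BILAG A or B flare will be calculated for each study arm by each body system and overall".

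The Analysis paragraph then says that the package used for the primary endpoint (effect estimates with 95% intervals, risk difference, and the summary of acceptable increase in risk against confidence) "will be performed for the probability of experiencing a BILAG A flare by Week 60". The paragraph returns to A or B for the visit counts: "The total number of visits that a subject has with a BILAG A or B flare will be summarized by treatment group and overall". A by-subject graph distinguishing A from B flares is also planned.

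SAP 7.3.4, the section on BILAG A flare, contains the same Analysis wording, and there it fits the endpoint. SAP section 12, item 3, says of 7.3.6: "This is a new endpoint was added to the SAP by the study team". It gives no further detail on the analysis.

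**The concern.** The variable that 7.3.6 defines and the event that its comparison names are different. A programmer who follows the Analysis sentence as written produces the A-only comparison a second time and no A-or-B risk difference, interval for that difference, or curve.

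A and A-or-B are not interchangeable. Every A flare counts in both, but A-or-B also takes in subjects whose worst grade was B, and Protocol 1.5 warns that false positive B flares are frequent with this instrument. The two comparisons could differ in size and in precision.

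What is at stake is mainly pre-specification. The endpoint is absent from the protocol. The trial is open-label, and Protocol 3.1.1 says that statistical staff at the coordinating center are unblinded. The SAP is therefore the only record of what was planned for this endpoint. If the sentence is corrected only after results are known, the A-or-B comparison is hard to present as planned in advance.

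**Working it through.** No arithmetic on trial figures applies: the point rests on no sample size, power, alpha or event count, and the plan states no figure to reproduce. The check is a comparison of text.

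**Step 1. Endpoint against analysis, for every SAP 7.3 section that borrows the primary-endpoint analysis.**

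| SAP section | Event defined under Endpoint | Event named under Analysis | Match |
|---|---|---|---|
| 7.3.2 | Any, and any severe, SELENA-SLEDAI flare | Same | Yes |
| 7.3.4 | BILAG A flare | BILAG A flare | Yes |
| 7.3.5 | BILAG renal A flare, renal subgroup | Same | Yes |
| 7.3.6 | BILAG A or B flare | BILAG A flare | **No** |
| 7.3.8 | Aggressive adjunctive or cytotoxic therapy | Same | Yes |

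Four of the five sections name their own endpoint. Only 7.3.6 names the endpoint of another section.

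**Step 2. What 7.3.6 plans for A or B.** Specified: the probability in each arm, by body system and overall; the number of visits with an A or B flare; summary tables by body system; and the graph by flare type. Not specified: the risk difference with its interval, and the confidence curve.

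**Step 3. Whether another section fills the gap.**
- SAP 7.3 sets a general rule: "Interval estimates will be generated at the 95% confidence level". It fixes a level. It does not say which contrast is to be estimated.
- Protocol 8.3.2.2 lists the probability endpoints to be analysed like the primary one. The BILAG entries are "any BILAG\* A flare by Week 60, a BILAG\* Renal A flare (for subjects with renal manifestations) by Week 60". A or B is not among them.
- The SAP synopsis, 7.5, 8.3 and section 12 contain no A-or-B risk difference or curve.

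**Step 4. Why the A-only result cannot stand in.** With simple proportions, a subject with an A or B flare either had at least one A flare or had B flares only. So, in each arm, P(A or B) = P(A) + P(B only). Subtracting maintenance from withdrawal gives RD(A or B) = RD(A) + RD(B only). The two risk differences agree only if the B-only risk is equal in the two arms. The documents give no rates from which to judge that.

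**Step 5. Likely origin.** SAP 7.3.9 to 7.3.12 still cite the SLICC/DI section as 7.3.6, although it is now 7.3.7. SAP 7.3.13.3 still cites Systemic Steroid Dose as 7.3.8, although it is now 7.3.9. Both are off by one, as expected if 7.3.6 was inserted late and the cross-references were not updated. The Analysis sentence was probably carried over from 7.3.4 at that point.

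**The case against.** The strongest reply is that this is a drafting slip with an obvious intent. The heading, the variable, the early-termination rule, the per-arm probability, the visit counts and the graph all say A or B. An analyst reading the whole section would most naturally apply the analysis to the variable just defined. The estimation method is fixed in SAP 7.2.2, and the populations and interval level in 7.3, so correcting one phrase leaves almost no analytic freedom. The point estimate of the difference is also only a subtraction of two probabilities that are already planned. The endpoint is exploratory, with no multiplicity adjustment.

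Most of this stands, and it limits the harm. It does not remove the mismatch: the Analysis sentence is an operative instruction, and it names the wrong event. That the intent can be guessed is a reason to correct the text.

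Two stronger readings are tempting, and the documents do not support either.
- A reader might infer that the A-or-B endpoint goes unanalysed, or that its comparison will certainly never be run. Descriptive A-or-B results are planned by arm, and the programmed analysis may follow the evident intent. The gap is in the text as literally read.
- A reader might infer from SAP section 12, item 4, that the full sample size was kept for A-or-B flares in particular. Item 4 says that "The larger sample size is necessary to improve precision for these important secondary endpoints", but it refers to BILAG and SELENA-SLEDAI flares in general and does not separate A from A-or-B. BILAG A, BILAG renal A and SELENA-SLEDAI flares each have a specified comparison.

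**Conclusion.** The point holds as a specification error in SAP 7.3.6, of limited consequence. Read literally, the plan specifies the BILAG A comparison twice (7.3.4 and 7.3.6) and gives the added A-or-B endpoint no risk difference with interval and no confidence curve. The primary analysis, the safety analyses and the other secondary comparisons are untouched.

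The effect on results cannot be quantified, because the documents report no BILAG A or A-or-B rates by arm. The conclusion assumes only that the sentence is applied as written. If the programs already use the A-or-B variable, the remaining problem is that the SAP does not document what was done. That the wording was carried over from 7.3.4 is an inference from the stale cross-references. The SAP does not state it.

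**What to change.** In the Analysis sentence of SAP 7.3.6, change the event from BILAG A flare by Week 60 to BILAG A or B flare by Week 60, matching the any-body-system variable defined in the same section. Make the change before the analysis is run. If the database has already been locked, record it in the clinical study report, as Protocol 8.5.6 requires for SAP changes after lock.

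The cost is one phrase. No new data are needed, and no analysis is added overall, since the corrected comparison replaces a duplicate. The outdated section numbers in 7.3.9 to 7.3.12 and in 7.3.13.3 can be corrected in the same revision.

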# 7.3.7. Changes in the SLICC/DI

**Endpoint**: The Systemic Lupus International Collaborating Clinics/American College of Rheumatology Disease Damage Index for Systemic Lupus Erythematosus (SLICC/DI) will be assessed at Baseline, Weeks 24, 48 and 60, and any Flare or Endpoint visits that occur during the course of the trial. Data for the SLICC/DI will be captured on the SLICC/ACR Damage Index for Systemic Lupus Erythematosus CRF page.

The SLICC/DI measures accumulated damage that has occurred since the onset of SLE, regardless of cause, in 12 organ systems. SLE damage is defined as an irreversible change in an organ or system that has been present for at least 6 months. The original SLICC/DI instrument includes an evaluation of proteinuria based on a 24-hour urine assessment. For this study, the protein:creatinine ratio will typically be derived from the spot urine assessment although a 24-hour urine may be used if the spot urine assessment is not available.

The SLICC/DI includes 39 areas of damage in 12 domains, where each item is rated as present or absent; if evidence of damage is present for a particular item, it is given a score of 1. Some items are scored with 2 or 3 points in the case of recurring events or end stage renal disease. The SLICC/DI total score will be computed as the sum of all scores for items indicated as present; scores can range from 0 to 45. Higher scores indicate more damage. Missing scores will not be imputed.

Change from baseline in the SLICC/DI score at Weeks 24, 48, and 60 will be computed for each subject.

Version: 1.0 Page 24 of 48

**Analysis**: Descriptive statistics (mean, standard deviation or standard error, median, minimum, maximum and number of subjects in a group) and 95% confidence intervals will be reported for the difference in the change from baseline in the SLICC/DI score between the treatment groups at each specified time point. The SLICC/DI score and change from baseline in will be shown graphically by treatment arm. Spaghetti plots and summary statistics including 25th percentile, mean, median, and 75th percentile will be plotted for each visit by treatment group.

# 7.3.8. The Addition of Aggressive Adjunctive Therapy to MMF or Change in MMF Therapy to Cytotoxic Drug Due to Flare

**Endpoint**: Medications are assessed at each study visit throughout the duration of the study and are collected on the *Prior/Concomitant Medications* CRF page.

For both the maintenance and withdrawal arms, the addition of aggressive adjunctive therapy can include IV immunoglobulin or rituximab at any point during the subject's participation in the study. A change in therapy to cytotoxic drug due to flare can include drugs such as cyclophosphamide, etc. A blinded list of study medications will be reviewed to identify the addition of aggressive adjunctive therapy or cytotoxic drugs.

For each subject, a yes/no variable will be created to indicate whether a subject added aggressive adjunctive therapy to MMF or changed MMF therapy to cytotoxic drug due to flare by Week 60. Subjects off MMF in the withdrawal arm will be included in the endpoint if aggressive adjunctive therapy or cytotoxic drugs were added to treat a flare. Subjects who terminate early from the study prior to adding aggressive adjunctive therapy to MMF or changing MMF therapy to cytotoxic drug due to flare will be categorized as not meeting the endpoint.

The probability of adding aggressive adjunctive therapy to MMF or changing MMF therapy to cytotoxic drug due to flare will be calculated for each study arm.

**Analysis**: Analyses analogous to those specified for the primary endpoint (effect estimates and 95% confidence intervals, risk difference, and summaries of increased risk ( $\alpha$ ) vs.% confidence the "true" risk is  $\leq \alpha$ ) will be performed for adding aggressive adjunctive therapy to MMF or changing MMF therapy to cytotoxic drug due to flare by Week 60. See Section 7.2.2, *Primary Analysis of the Primary Endpoint*, for more details on the analyses. Additionally, type of new therapy will be summarized by treatment arm and overall.

# 7.3.9. Systemic Steroid Dose

**Endpoint**: Medications, including steroid use, are assessed at each study visit throughout the duration of the study and are collected on the *Prior/Concomitant Medications* CRF page.

Steroids include medications that code to a medication class which includes the terms "glucocorticoid" or "corticosteroid". Systemic steroids will include any of these steroids that are taken by mouth (PO), intravenous (IV), or intramuscular (IM).

Total cumulative systemic steroid dose, in milligrams, will be summarized over the 60 week study period, or until early study termination, for each subject. Total cumulative systemic steroid dose, in milligrams, given specifically to treat a SLE flare may also be summarized.

Additionally, the excess steroid dose given over the course of the 60 week study period, or until early study termination, will be calculated for each subject. Excess steroid dose will be

Version: 1.0 Page 25 of 48

calculated based on the difference between expected steroid dose (extrapolated from baseline steroid dose) and actual total cumulative steroid dose given during the course of the study.

**Analysis**: Analyses analogous to those specified in Section 7.3.6, *Changes in the SLICC/DI*, will be performed on the total steroid dose and excess steroid dose at Week 60.

# 7.3.10. Changes in the FACIT Score

**Endpoint**: The Functional Assessment of Chronic Illness Therapy (FACIT) fatigue scale will be assessed at Baseline, Weeks 24, 48 and 60, and any Flare or Endpoint visits that occur during the course of the trial. Data for the FACIT fatigue scale will be captured on the FACIT CRF page.

The FACIT fatigue scale assesses fatigue in subjects with chronic illness. Thirteen fatigue-related questions are measured on a 4-point scale. The FACIT fatigue subscale scoring guide (see Appendix 14.5, FACIT-Fatigue Subscale Scoring Guidelines) identifies those items that must be reversed before being added to obtain subscale totals. Negatively stated items are reversed by subtracting the response from "4". After reversing proper items, all subscale items are summed to a total, which is the subscale score. High scores represent less fatigue and better quality of life.

If there are missing items, subscale scores can be prorated. This is done by multiplying the sum of the subscale by the number of items in the subscale, then dividing by the number of items actually answered. This can be done on the scoring guide or by using the formula below:

**Prorated subscale score =** [Sum of item scores] **x** [N of items in subscale] ÷ [N of items answered]

When there are missing data, prorating by subscale in this way is acceptable as long as more than 50% of the items were answered (e.g., a minimum of 7 of 13 items).

Change from baseline in the FACIT score at Weeks 24, 48, and 60 will be computed for each subject.

**Analysis**: Analyses analogous to those specified in Section 7.3.6, *Changes in the SLICC/DI*, will be performed on the FACIT score.

#### 7.3.11. Changes in SF-36 Scores

**Endpoint**: The Short Form Health Survey (SF-36) will be assessed at Baseline, Weeks 24, 48 and 60, and any Flare or Endpoint visits that occur during the course of the trial. Data for the SF-36 will be captured on the *SF-36 Survey* CRF page.

The SF-36 is a 36-item, patient-reported survey of patient health. Higher scores indicate better outcomes while lower scores indicate more disability.

The following SF-36 scale scores will be calculated: Physical Functioning, Role-Physical, Bodily Pain, General Health, Vitality, Social Functioning, Role-Emotional, and Mental Health. From these scale scores, two summary scores that aggregate measures will be created. The Physical Component Score is comprised of the Physical Functioning Scale, the Role-Physical Scale, the Bodily Pain Scale, and the General Health Scale. The Mental Component Score is comprised of the Vitality Scale, the Social Functioning Scale, the Role-Emotional Scale, and the Mental Health Scale.

Version: 1.0 Page 26 of 48

Norm-based scores will also be generated for the eight SF-36 scales and the two summary measures. All eight SF-36 scales and the two summary scores will be normalized to have a mean of 50 and a standard deviation of 10 for the 1998 general US population. The advantage of the standardization is that results for one scale can be meaningfully compared with the other scales, and the scores have a direct interpretation in relation to the distribution of scores in the 1998 general US population. Specifically, scores above or below 50 are above or below the average, respectively, for the 1998 general US population. Because the standard deviation is 10 for all 8 scales, each one point difference in scores is equivalent to one-tenth of a standard deviation unit or an effect size of 0.10. See Appendix 14.6, *Scoring the SF-36 Version 2*, of this SAP for details regarding calculation of these scores.

Change from baseline in the SF-36 Physical Functioning (PF) and Physical Component Summary (PCS) domains at Weeks 24, 48, and 60 will be computed for each subject.

**Analysis**: Analyses analogous to those specified in Section 7.3.6, *Changes in the SLICC/DI*, will be performed on the SF-36 PF and PCS.

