### 3.1.1 Stratification, Randomization, and Blinding

Subjects will be randomized in a 1:1 ratio to either continue or withdraw from MMF. Given the relatively small number of subjects expected per site and the importance of ensuring balance on key disease-defining characteristics an adaptive procedure based on Frane [31] minimization concepts will be used to increase the likelihood of balance in treatment arms. The baseline characteristics that will be considered are study site, disease manifestation (renal disease, which will include subjects who presently have renal disease as well as those who have had renal manifestations in the past, versus non-renal disease, which will include subjects who have never had renal disease), and baseline MMF dose (< 2000 mg per day versus  $\geq 2000$  mg per day).

Subjects and investigational staff responsible for clinical care will not be blinded to the randomized treatment assignment. The cumbersome scheme that would have been needed to maintain the blind required that subjects take different numbers of pills from multiple bottles. Implementation of the scheme would have placed undue burden on the subjects and had a high potential for dosing errors. Knowledge of the assigned treatment also has the advantage of facilitating rapid response in the event of a serious flare.

Unblinding the trial has the potential to impact the estimated rates of disease reactivation, because the definition of this endpoint includes subjective elements. In order to assess the magnitude and direction of the impact on these estimates, a second blinded clinician will also conduct the physical exams scheduled for Weeks 8, 12, 16, and 20. If at Week 20, the subject has a mild/moderate or severe SELENA-SLEDAI flare, the blinded physician should also participate in the Week 24 visit. These time points were selected, because we anticipate that most flares will occur early in the study. The blinded physician will also receive any additional blinded subject records needed to complete the SELENA-SLEDAI and a questionnaire about the need to change medications. This information will be used to compare the rate of disease reactivation among blinded and unblinded assessors.

Statistical and project staff at the SACCC and the DAIT Medical Monitor and Project Manager will be unblinded to individual treatment assignments as well.

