#### **8.5** Other Statistical Considerations

#### 8.5.1 **Covariates**

Covariates that may be considered include, but are not limited to:

- Age
- Race/ethnicity
- SLE duration
- MMF dose at baseline
- MMF use (cumulative mg-year)
- HCQ use (cumulative mg-year)
- Historical organ involvement
- Serological activity at entry (depletion of C3 or C4, presence of dsDNA antibodies)
- Steroid dose at entry
- Disease activity at entry (m-SLEDAI)
- Disease damage at entry, SLICC/ACR Damage Index (SDI)

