# 7.3.12. Change in Lupus QoL Score

**Endpoint**: The Lupus Quality of Life (QoL) instrument will be assessed at Baseline, Weeks 24, 48 and 60, and any Flare or Endpoint visits that occur during the course of the trial. Data for the Lupus QoL will be captured on the *Lupus QoL* CRF page.

The Lupus QoL assessment is a 34 item questionnaire across 8 domains that is designed to find out how SLE affects a subject's life over the preceding 4 weeks. The physical health domain comprises item numbers 1–8, pain comprises 9–11, planning comprises 12–14, intimate relationships comprises 15 and 16, burden to others comprises 17–19, emotional health comprises 20–25, body image comprises 26–30, and fatigue comprises 31–34. Each of the 34 questions are answered on a 5-point scale, where 0 = all of the time, 1 = most of the time, 2 = a good bit of the time, 3 = occasionally, and 4 = never.

Item response scores are totaled for each domain and the mean raw domain score is obtained by dividing the total score by the number of items in that domain. The mean raw domain score is transformed to scores ranging from 0 (worst QOL) to 100 (best QOL) by dividing by 4 (the number of Likert responses [5 responses] minus 1) and then multiplying by 100, as below:

$$\frac{\text{mean raw domain score}}{4} \times 100 = \text{transformed score for domain}$$

Transformed domain scores are obtainable when at least 50% of the items are answered. The mean raw domain score is then calculated by totaling the item response scores of the answered items and dividing by the number of answered items. A nonapplicable response is treated as unanswered and the domain score is calculated as above.

Change from baseline in the Lupus QoL scores at Weeks 24, 48, and 60 will be computed for each subject.

**Analysis**: Analyses analogous to those specified in Section 7.3.6, *Changes in the SLICC/DI*, will be performed on the Lupus QoL scores.

Version: 1.0 Page 27 of 48

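### Quality-of-life and fatigue differences between arms are planned as change scores with no covariate; adjusting for the baseline score already collected would usually narrow the intervals

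*SAP*

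**What the plan says.** SAP 7.3.10 to 7.3.12 define the three endpoints in the same way. For FACIT: "Change from baseline in the FACIT score at Weeks 24, 48, and 60 will be computed for each subject". For the SF-36: "Change from baseline in the SF-36 Physical Functioning (PF) and Physical Component Summary (PCS) domains at Weeks 24, 48, and 60 will be computed". For Lupus QoL: "Change from baseline in the Lupus QoL scores at Weeks 24, 48, and 60 will be computed for each subject". Each section then points to the SLICC/DI analysis in SAP 7.3.7, which plans descriptive statistics plus an interval for the arm comparison at every visit: "95% confidence intervals will be reported for the difference in the change from baseline in the SLICC/DI score between the treatment groups at each specified". Protocol 8.3.2.2 has the same method: "95% confidence intervals will be reported for the difference between the treatment groups in cumulative steroid dose at Week 60; change in FACIT fatigue score", followed by the other scales. All three instruments are administered at baseline.

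Three other places bear on the point, and none of them settles it:

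- Protocol 8.5.1 is permissive: "Covariates that may be considered include, but are not limited to" a list that has baseline MMF dose on it but no baseline FACIT, SF-36 or Lupus QoL score.
- The Data Analyses paragraph of both synopses promises model-based contrasts within the secondary analyses, but names no endpoint, model or covariate.
- The only regression model named anywhere is Poisson regression for the secondary safety endpoints (Protocol 8.3.1, SAP 8.3.1).

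**The concern.** Subtracting the baseline score fixes its coefficient at 1. A regression on the baseline score estimates that coefficient and, in large samples, never has the larger variance. The plan therefore usually gives up some precision that the collected data could supply.

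Minimisation does not remove the issue. Protocol 3.1.1 says "The baseline characteristics that will be considered are study site, disease manifestation" and baseline MMF dose group; the questionnaire scores are not balanced by design. Where the arms differ at baseline by chance, the change-score estimate is shifted by (1 − ρ) times that difference when the SDs are equal, with ρ the baseline-to-follow-up correlation. This is the same loss of precision seen from a particular sample. It is not a second loss to add to the first.

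The effect of withdrawal on quality of life is a secondary objective (Protocol 2.2.1), and Protocol 8.3.2.1 counts quality of life among the things to weigh against flare risk. Tighter intervals on these scales would help that purpose. Validity and the primary result are not affected.

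**Working it through.** The plan states no power, SD or interval width for these scales, so there is no figure of its own to reproduce. Protocol Table 8.1 concerns the primary endpoint and does not bear on this point.

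**Inputs**

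- 120 subjects randomised 1:1, so 60 per arm (study design, both documents). Complete data at each visit is assumed, which is a best case.
- 95% intervals (SAP 7.3), taken as two-sided.
- SD of 10 points at baseline and follow-up. SAP 7.3.11 says the SF-36 scores "will be normalized to have a mean of 50 and a standard deviation of 10 for the 1998 general US population". This is a population norm, used for illustration only.
- ρ is not given. Values of 0.5, 0.7 and 0.9 are assumed.

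**Formulas**

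Change score: half-width = t(118) × 10 × √(2(1 − ρ)) × √(2/60).

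Adjusted for baseline score, renal status and dose group: half-width = t(115) × 10 × √(1 − ρ²) × √(2/60) × c. Here c = √(1 + 1/116) if minimisation balances the two factors, and c = √(1 + 3/114) if they are balanced only at random.

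The constants are t(118) = 1.9803, t(115) = 1.9808 and √(2/60) = 0.1826; c is 1.0043 or 1.0131.

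**Worked case, ρ = 0.5, factors balanced**

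- Change score: 1.9803 × 10 × 1.0000 × 0.1826 = 3.62.
- Adjusted: 1.9808 × 10 × 0.8660 × 0.1826 × 1.0043 = 3.15.
- The adjusted interval is 13.0% narrower.

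**Equal SDs**

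| ρ | Change score | Adjusted, balanced | Narrower by | Adjusted, random | Narrower by |
|---|---|---|---|---|---|
| 0.5 | 3.62 | 3.15 | 13.0% | 3.17 | 12.2% |
| 0.7 | 2.80 | 2.59 | 7.4% | 2.62 | 6.6% |
| 0.9 | 1.62 | 1.58 | 2.1% | 1.60 | 1.2% |

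A simulation of 4,000 trials gave half-widths within 0.01 of these, with coverage of 94.6% to 95.0% for every method.

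**Unequal SDs**

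If the follow-up SD is k times the baseline SD, the width ratio before the small-sample cost is k√(1 − ρ²) / √(k² + 1 − 2ρk). After the cost, the reduction in width is as follows (minus means wider):

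| k | ρ | Balanced | Random |
|---|---|---|---|
| 0.8 | 0.5 | 24.1% | 23.4% |
| 0.8 | 0.7 | 20.4% | 19.7% |
| 0.8 | 0.9 | 21.7% | 21.0% |
| 1.25 | 0.5 | 5.1% | 4.2% |
| 1.25 | 0.7 | 0.5% | −0.4% |
| 1.25 | 0.9 | 2.1% | 1.2% |
| 1.1 | 0.9 | −0.4% | −1.3% |

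The percentages are free of the measurement scale, so they carry over to FACIT and Lupus QoL for the same ρ and k.

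**Cost if the covariates explain nothing.** Compared with a follow-up comparison that has no covariates, the width is multiplied by (1.9808/1.9803) × c, which is 0.5% wider (balanced) or 1.3% wider (random).

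**Chance imbalance.** The standard error of the baseline difference is 10 × √(2/60) = 1.83 points. A difference of that size shifts the change-score estimate by (1 − ρ) × 1.83 = 0.91, 0.55 or 0.18 points at ρ = 0.5, 0.7 or 0.9.

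**The case against.** The planned method is unbiased, consistent across the two documents, and applied to endpoints that carry no test, threshold or power claim. With equal SDs the half-width falls by only 0.47, 0.21 or 0.04 SF-36 points (3.62 − 3.15, 2.80 − 2.59, 1.62 − 1.58), and SAP 7.3.11 equates one point with an effect size of 0.10. The correlation and SDs are unknown. Because entry selects quiescent, stable subjects and flares are expected later, a follow-up SD at or above baseline is at least as plausible as one below it, and there the gain is small or nil. The word unadjusted does not appear in the SAP; it is inferred from the absence of a covariate. The SAP is final, and coordinating-centre statisticians are unblinded (Protocol 3.1.1).

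Much of this stands, and it sets the strength of the point: an optional improvement, stated as usual and not certain. It does not remove the point. The general wording on model-based contrasts and optional covariates is never carried into 7.3.7 or 7.3.10 to 7.3.12, so a reader of those sections would compute plain change-score differences.

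A further challenge is that the missing-data rule in Protocol 8.5.5 fits an available-case analysis as well as a repeated-measures model. The rule treats missing values as random and imputes none, and a likelihood-based repeated-measures model is a fair reading of that. How much the model would recover is unknown. Subjects who stop treatment should complete their remaining visits where possible (Protocol 5.10.1.1), and those who withdraw are asked for a Week 60-type assessment (Protocol 5.10.2.1 and 6.4.4.4).

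**Conclusion.** The point holds as a suggestion, not a required correction. With 60 per arm, complete data and equal SDs, adjustment would narrow the 95% intervals for FACIT, SF-36 PF/PCS and Lupus QoL by about 13% at ρ = 0.5, 7% at 0.7 and 2% at 0.9 if the two factors are balanced, and by about one percentage point less if they are not. Over the SD ratios examined, the result runs from 24.1% narrower to 1.3% wider. These figures are for a single visit; with complete data a repeated-measures model gives essentially the same per-visit estimates. They credit renal status and dose group with no prognostic value, so any they have would add to the gain. Confidence is high in the reading of the plan and the arithmetic; the size of the benefit in this trial cannot be known from the documents.

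**What to change.** For FACIT, SF-36 PF and PCS, and each Lupus QoL domain, add a repeated-measures model for the Week 24, 48 and 60 scores. Include arm, visit, arm by visit, baseline score, baseline by visit, renal status and MMF dose group, with an unstructured covariance. Leave out site, in line with SAP 7.1.1. Report the adjusted difference and 95% interval at each visit in the mITT and per-protocol populations, and keep the planned raw change summaries. State how early-withdrawal, flare and endpoint questionnaires map to visits, and give a fallback covariance if the model does not converge.

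Say in the SAP that this is the contrast meant by the synopsis sentence on model-based approaches, and list it in SAP section 12 as an added analysis. In the same revision, correct the cross-reference in SAP 7.3.9 to 7.3.12, which cites 7.3.6 for the SLICC/DI method; that section is 7.3.7. The Kaplan-Meier primary analysis is unchanged.

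The cost is a revision of SAP version 1.0, which Protocol 8.5.6 allows, and modest programming, with no extra data, visits or subjects. Because coordinating-centre statisticians know the assignments, the model should be fixed in writing before database lock and before these scores are tabulated by arm.
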